10.9.2 Vital Signs

The subject will undergo an assessment of blood pressure using a blood pressure recording device with an appropriate cuff size and with the subject in a sitting position. It is recommended that the subject rests for at least 5 minutes prior to this measurement. The same arm will be used for all measurements. Pulse rate, respiratory rate, and body temperature will also be measured.

The Investigator will perform an overall evaluation for safety purposes and the recording will be reported as 'normal', 'abnormal clinically significant (CS)', or 'abnormal not clinically significant (NCS)'.

Abnormalities of clinical significance will be reported as AEs. Repeat measurements will be performed if needed.

10.9.3 Electrocardiogram

A 12-lead ECG will be performed after the subject has rested for at least 5 minutes in the supine position. The Investigator will perform an overall evaluation of the ECG for safety purposes and the recording will be reported as 'normal', 'abnormal CS', or 'abnormal NCS'. Abnormalities of clinical significance will be reported as AEs. Repeat measurements will be performed if needed.

10.9.4 Nevi Evaluation

Nevi will be assessed at the specified timepoints shown in the schedule of assessments (Table 9-1). Baseline nevi evaluation will be conducted at any time (Visit 1 or 2) before randomization.

Nevi will be assessed locally by a visual full body examination performed by a dermatologist or other qualified site staff. Any subject with suspicious nevi of clinical concern will have treatment temporarily discontinued and be referred for further nevi evaluation (e.g., biopsy), as deemed necessary by the dermatologist or other qualified site staff.

Any biopsy samples collected during the study will be sent for evaluation to the central pathology lab. If there are any clinically significant adverse findings from the biopsy, subjects will not be allowed to resume study drug and will be discontinued from study treatment. Adverse change must be demonstrated histologically and confirmed by central pathologist. Visual evaluation of change will not be acceptable criteria for complete discharge from treatment. If central assessment determines that lesion or nevi is benign, and the findings are not clinically significant, subject will be allowed to resume study treatment at the same dose when study drug was interrupted. Clinical sites will have access to a centralized dermatology specialist with experience on nevi. The centralized dermatology specialist will be available to communicate with the Investigator, dermatologist and/or qualified staff on the changes of any expected potential changes in nevi and advice on the process management prior and after biopsy.

The results will be recorded in the source documents and the eCRF as well as shared and discussed with the subject. Nevi of clinical concern must be recorded as AE.

Nevi assessment details will be fully described in a separate document.

10.9.4.1 Central Pathology Laboratory

Central pathology laboratory details will be fully described in a separate document.

10.9.5 Routine Laboratory Evaluations

Blood and urine samples will be collected for routine clinical laboratory safety evaluations according to the schedule of assessments (Table 9-1).

The specific laboratory parameters evaluated during the study are presented in Table 10-1.

10.9.5.1 Hepatic Markers

At Visits 3, 5, 8, and 9, subjects may undergo mobile laboratory or in-clinic visits for sample collection to measure biochemistry (liver function) markers (ALT, AST, GGT, ALP, direct and total bilirubin). Blood samples for liver function markers will be shipped to the central laboratory and the central laboratory will measure the liver markers.

10.9.5.2 Additional Laboratory Assessments

Additional laboratory safety evaluations will be performed at other times, if judged to be clinically appropriate, or if the ongoing review of the data suggests a more detailed assessment of laboratory safety evaluations is required. Any changes to the scheduled times of laboratory safety tests will be agreed with the Sponsor and documented in the Trial Master File.

The Investigator will perform a clinical assessment of all laboratory safety data. The Investigator will record the assessment as 'normal', 'abnormal CS', or 'abnormal NCS'. Lab test abnormalities of clinical significance will be reported as AEs. Repeat lab tests or measurements will be performed if needed.

If subjects will meet treatment withdrawal criteria for elevated liver function tests, the subjects should be treated using standard of care as directed by the Investigator and followed until resolution (Section 8.5).

Table 10-1 Routine Laboratory Evaluations

Hematology:	
Hemoglobin	Mean corpuscular hemoglobin
Hematocrit	Mean corpuscular hemoglobin concentration
Platelet count	Mean corpuscular volume
Red blood cell count	White blood cell count and differential
Biochemistry:	
Alkaline phosphatase	Cholesterol
Aspartate aminotransferase	Triglycerides
Alanine aminotransferase	High-density lipoprotein cholesterol
Gamma-glutamyl transpeptidase	Low-density lipoprotein cholesterol
Potassium	Protein (total)
Sodium	Albumin
Chloride	Creatine kinase
Inorganic phosphate	Creatinine
Glucose	Ferritin
Bilirubin (direct and total)	Vitamin D
Blood urea nitrogen	
Coagulation:	
Prothrombin time	Activated partial thromboplastin time
International normalized ratio	
Urinalysis:	
Specific gravity, pH, protein, glucose, ketones, urobilinogen, blood	
Microscopic examination ^a	

^a Performed only if required, based on urinalysis results

Blood and urine samples will be analyzed by the central laboratory and/or specialized laboratory where applicable using standard methods. Procedures for the handling of samples will be described in full in a separate document.

10.9.6 Pharmacogenomics

Blood samples will be collected for PGx analysis for those subjects who have given their consent/assent for optional PGx analysis at Visit 2.

[REDACTED] Samples may be retained for future research use in genetic analysis for EPP or XLP and/or any efficacy/safety concern occur.

Sample handling processing of PGx samples will be described fully in a separate laboratory manual.

10.9.7 Porphyrin and Protoporphyrin Levels

Plasma total porphyrins and erythrocyte protoporphyrin will be assessed at Visits 1, 4, 6, 7, 10, and 11.

11 STUDY TREATMENT

11.1 Investigational Medicinal Product

11.1.1 Drug Product

MT-7117 and matching placebo [REDACTED] are light-orange, [REDACTED] with no identifying marks. MT-7117 [REDACTED] contain [REDACTED] of active drug product (its free-base form). The matching placebo [REDACTED] will be manufactured to be physically identical to the MT-7117 [REDACTED]. All MT-7117 [REDACTED] and the matching placebo [REDACTED] will be manufactured, tested, and released according to Good Manufacturing Practice (GMP).

A bulk supply of MT-7117 [REDACTED] and matching placebo [REDACTED] will be packed into [REDACTED], placed into [REDACTED] [REDACTED] and shipped to [REDACTED] for packaging into finished Investigational medicinal product (IMP).

Individual subject doses will be packed in [REDACTED] using [REDACTED], then labeled and released from [REDACTED] according to GMP. [REDACTED] will perform Qualified Person (QP) certification of the finished IMP for use in the UK. [REDACTED] will perform Qualified Person (QP) certification of the finished IMP for use in the EU. All labeling will comply with applicable regulatory requirements.

11.1.2 Study Drug Supply

The Sponsor will provide MT-7117 and placebo [REDACTED] in [REDACTED] to each site, for each subject, for the duration of their participation in the study. The Interactive Web-based Response System (IWRS) will allocate sufficient uniquely-numbered, blinded [REDACTED], to be dispensed by the Investigator, study nurse or hospital pharmacist, according to the subject's randomized treatment group (MT-7117 [REDACTED], [REDACTED], or placebo) and study visits. Each subject will take 2 [REDACTED] per day with or without food.

Subjects will be instructed to bring their study medication with them to each visit. Subjects will return all study medication that may remain in their possession to the study staff at the end of treatment visit. In cases where subjects forget to return to the clinic with their [REDACTED], sites will be instructed to inquire as to the subjects daily dosing compliance, capturing total number of days missed. Subjects will be instructed to return medication packaging and empty [REDACTED] at the follow up visit.

11.1.3 Formulation, Packaging, Site Storage, and Labeling (MT-7117)

Study medication [REDACTED] will be provided in 2 strengths: 0 mg (placebo) and [REDACTED] (MT-7117) [REDACTED]. Study medication will be provided to the study sites in labeled [REDACTED]. All study medication should be stored according to the IMP clinical label.

Required study site documentation for MT-7117 [REDACTED] will include, but may not be limited to, the following information:

- Receipt date.
- Description of medication package, and medication product.
- Lot number or code/Batch number or code.
- Expiration and manufacturing dates.
- Dispensing information.
- Investigational New Drug Application (IND) number.
- Certificate of compliance.

11.1.4 Shipping, Receipt, Handling and Storage

On receiving a shipment of finished study medication at the Investigator site, the Investigator or designee will conduct an inventory check and complete a supplies-receipt document, the original of which will be retained at the Investigator site. In addition, a copy must be returned to the Sponsor or designee. The Investigator or designee will maintain a record of all study medication received and returned.

Study medication at the Investigator site will be stored according to the conditions stated on the IMP clinical label in a locked, restricted-access area. A temperature log recording the daily continuous temperature of the storage area will be maintained (including weekends). Any study medication storage temperature deviations will be reported to the Sponsor as soon as possible.

11.1.5 Dispensing

At each visit, the Investigator or designee will provide the subject with the allocated dose. A record of the study medication dispensed to each subject will be maintained by the Investigator or designee in an Investigational Product Accountability Log. Dispensed study drug will not be re-allocated to a subject.

In the cases where subject encounters a missed visit that renders a subject without sufficient medication to maintain daily dosing (e.g., a subject resides out of state relative to the Investigator's location and experiences a travel conflict), the site may ship an additional [REDACTED] to the subject upon written Sponsor approval. In these instances, the Sponsor [and/or the Contract Research Organization (CRO) designee] will assist the site to ensure the process is documented appropriately. Shipments made in these rare instances will require that IMP be maintained within the required temperature range along with confirmation of receipt by the study subject. This process will not be allowed where site policies prohibit it. Subjects should return to the clinical site to complete the scheduled visit, required assessments, and to have study medication dispensed.

11.1.6 Study Medication Accountability

The Investigator or designee must maintain an accurate record of the shipment and dispensing of study medication in an Investigational Product Accountability Log. Medication accountability will be noted by the field monitor during site visits and at the completion of the study. Subjects will be asked to return all unused study medication and packaging on a regular basis, at the end of the study or at the time of study treatment discontinuation.

11.1.7 Disposal and Destruction

At study close-out, and as appropriate during the course of the study and only once full accountability has taken place, the Investigator will return all used and unused study medication, packaging, medication labels, and a copy of the completed Investigational Product Accountability Log to the Sponsor's designated monitor or to the address provided in the Investigator Binder at each site.

The study medication supply may be destroyed at the designated Sponsor facility or third party, only once authorization to destroy has been given by the Sponsor. Sites with documented drug destruction procedures and facilities may destroy drug on site only once authorization to destroy has been given by the Sponsor.

11.2 Dosing

Subjects are to self-administer study medication - 2 █ once daily in the morning with or without food given as PI advice.

MT-7117 and/or placebo █ should be swallowed whole with approximately 240 mL of water (subjects may drink an additional 240 mL of water if they have difficulty swallowing the █). The █ are not to be chewed, crushed, dissolved, or divided.

11.3 Compliance

The prescribed dosage, timing, and mode of administration of study medication will not be changed. Subjects will be asked questions regarding the compliance, any departures from the intended regimen will be recorded in the eCRF.

Study medication accountability and subject compliance will be documented throughout the double-blind treatment period using study-specific study medication dispensing and return record forms. For subjects who do not return their █, the site will question each to determine compliance (e.g. number of doses missed since the last visit).

Subjects will be asked to return all unused medication including empty and partially used █. Study medication dispensed at the previous visit will be retrieved by the Investigator or designee and compliance assessed by returned medication count.

Non-compliance will be defined as taking $\leq 80\%$ or $\geq 120\%$ of study medication during any evaluation period (from any visit to the following visit).

11.4 Subject Identification

Each subject will be assigned a unique subject number at the screening visit. At Randomization, each subject will receive a unique randomization number. Both the subject number and the randomization number will be documented in the subject's source documents. The subject number will be used to identify subjects in the study.

A list identifying the subjects by their subject number will be kept at the Investigator site. The randomization numbers will be stored in IWRS database until the database lock.

11.5 Procedures for Assigning Subjects to Treatment Groups

Randomization will take place after confirmation of inclusion/exclusion criteria before the first administration of study medication on Day 1. Subjects will be randomly allocated on a 1:1:1 basis to 1 of 3 treatments (Section 7.1). For subjects with [REDACTED] subjects will be randomized to placebo or [REDACTED] in a 1:2 ratio.

[REDACTED] eDiary data will be used to generate the stratum. A minimum of 7 days of outside exposure data is required within the 14 days prior to randomization.

If study subjects elect to participate in the 26-weeks DBE after end of Visit 7 (EOT/Rand), subjects will remain blinded and subjects will be re-randomized. Subjects that received MT-7117 during the blinded period will continue the DBE in the same treatment arm and remain blinded. Subjects that received placebo will be randomized to receive MT-7117 [REDACTED] or [REDACTED] in 1:1 ratio for the 26 weeks DBE period. For subjects with [REDACTED] the [REDACTED] dose will be administered without re-randomization and will not be blinded during the extension period.

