7 INVESTIGATIONAL PLAN

7.1 Overall Study Design

This is a Phase 3, randomized, double-blind, placebo-controlled study to assess the efficacy, tolerability, and safety of MT-7117 in adults and adolescents with EPP or XLP. The study consists of a 6-week screening period, a 26-week double-blind treatment period, an optional 26-week double-blinded extension (DBE) period, and a 6-week follow-up period at Week 58 (or Week 32 if DBE is not elected). The total participation period is approximately 64 weeks.

The study design is illustrated in Figure 7-1.

Subjects will attend the screening visit (Visit 1) up to 6 weeks before Randomization (Visit 2), in order to confirm eligibility and obtain pre-study safety assessments including nevi evaluation. Subjects will also be instructed how to use an electronic sunlight exposure diary (SED).

At Visit 2, subjects meeting eligibility criteria with body weight ≥ 45 kg will be randomized in a 1:1:1 ratio to receive MT-7117 [REDACTED], or placebo in a double-blind manner.

The first dose will be administered at Visit 2 following baseline assessments including an in-clinic sunlight exposure test at any time before randomization (Visit 1 or 2), and melanin density determination before randomization (Visit 2). Active or placebo [REDACTED] will be administered once daily in the morning with or without food.

Subjects will subsequently attend in-clinic visits at Weeks 4 and 12 (Visits 4 and 6, respectively) during which assessments will be performed. In addition, subjects may undergo mobile laboratory or in-clinic visits for sample collection at Weeks 2 and 8 (Visits 3 and 5, respectively) to measure liver function markers (AST, ALT, GGT, ALP, direct and total bilirubin).

Subjects will attend the end of treatment visit at Week 26 or early termination visit (Visit 7 or Visit 11).

PK will be collected at scheduled visits for ≥ 18 to ≤ 75 -year-olds. For ≥ 12 to ≤ 17 -year-old subjects, a total of 9 PK samples at 3 time points will be collected: Day 1 (Visit 2) at 2, 4, 6, and 8 hours post-dose, Week 12 (Visit 6) at pre-dose and 3 hours post-dose, and Week 26 (Visit 7) at pre-dose and 2, and 4 hours post-dose.

Subjects will be offered participation in a 6-month extension where all participants are on active drug but are double-blinded to dose starting immediately after the end of the 26-week double-blind treatment period. If study subjects elect to participate in the 26-week DBE after end of

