14.2 Sample Size Estimation

For the primary estimand, the sample size of 159 is expected to provide adequate power for the comparisons between MT-7117 and placebo for change from baseline in the average daily sunlight exposure time (minutes) to first prodromal symptom associated with sunlight exposure between 1 hour post-sunrise and 1 hour pre-sunset at Week 26 based on the MT-7117-A01 study. The calculation of sample size assumes a 2-sided alpha level of 0.05 and a 20% dropout rate up to Week 26. The sample size of 42 completers per treatment group will provide 91% and 79% power to detect an effect size of 0.72 and 0.66 in the average daily time (minutes) to first prodromal symptom associated with sunlight exposure between 1 hour post-sunrise and 1 hour pre-sunset at Week 26 (ie, an absolute treatment difference of 57 mins between MT-7117 [REDACTED] [REDACTED] vs placebo, 52 mins between MT-7117 [REDACTED] [REDACTED] vs placebo, and a standard deviation [SD] of 79.3 mins). The sample size of 42 completers was calculated by SAS simulation using the fixed sequence testing procedure in order to confirm the power affected by multiplicity adjustment in treatment comparison for primary endpoint. Taking into account for a 20% dropout rate up to Week 26, total sample size of 159 was calculated.

Due to the rapid enrollment rate in the last few months of the enrollment period after COVID-19 restrictions were lifted in many countries, a total of 184 subjects were enrolled.

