8.1.5 Demographic and Other Baseline Characteristics

The following demographic and other baseline characteristics will be used.

	Category	Descriptive
Sex	Male, Female	
Age (years)	Adolescent(<18) Adult(18 – 65, >65)	Yes
Height (cm) at screening visit		Yes
Weight (kg) at screening visit	<45 ≥45	Yes
BMI (kg/m2)	[REDACTED]	Yes
Race	White, Black or African American, Asian(Japanese), American Indian or Alaska Native, Native Hawaiian or Pacific Islander, Other	
Country	US, Australia, Canada, Germany, Italy, Japan, Norway, Spain, Sweden, United Kingdom (from IWRS data)	
Region (Randomization stratification factor)	North America, Rest of world (Europe, Japan, Australia) (from IWRS data)	
Ethnicity	Hispanic or Latino, Non-Hispanic or Latino	
EPP/XLP	EPP, XLP	
Protoporphyrin (PPIX level) (mcg/dL)		Yes
Disease duration (years)		Yes
Baseline average daily time to first prodromal symptom (Randomization stratification factor)	[REDACTED]	
Actual baseline average daily time to first prodromal symptom	[REDACTED] [REDACTED]	Yes
Seasonality 1	Randomized in Spring and Summer inclusive, Other	

	(Spring and Summer: between September 1st to February 29 in Australia or between March 1st and August 31th in the other countries)	
Seasonality 2	Week 26 visit in Spring and Summer inclusive, Other (Spring and Summer: the date of Week 26 analysis visit is between September 1st and February 29th in Australia or the date of Week 26 analysis visit is between Mar 1st and August 31th in the other countries)	
Melanin density		Yes
Fitzpatrick skin type	I, II, III, IV, V-VI	
		

Demographic and other baseline characteristics will be summarized on the ITT1, ITT2, SAF1, and SAF2 populations. Demographic and other baseline characteristics will be summarized on the ITT1, ITT2, SAF1, and SAF2 populations by region (North America, Europe, Japan, Australia).

Demographic and other baseline characteristics will be listed on the RAND population.

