8.2.2 Secondary Efficacy Endpoints

The secondary endpoint PGIC at Week 26 will be analyzed using the similar model as specified for the primary analysis (MMRM) replacing the average daily sunlight exposure time to first prodromal symptom baseline covariate with PGIS covariates at baseline visit.

The change from baseline for total score in each domain of physical function and pain intensity in the PROMIS-57 at Week 26 will be analyzed in the same way.

For the total number of sunlight-induced pain events defined as prodromal symptoms with pain rating of 1-10 on the Likert scale during the 26-week double-blind treatment period, the negative binomial regression model with log link will be used. The model will include treatment and the randomization stratification factors as fixed effect. The estimated incidence rate (IR) and its 95% confidence interval for each treatment group, incidence rate ratio (IRR) of each active MT-7117 treatment group versus placebo, 95% confidence interval of the IRR together

with relevant p-values will be reported.

The following example SAS code will be used;

[REDACTED]

The percentage of subjects who are responders based on average daily sunlight exposure time to first prodromal symptom associated with sunlight exposure between 1 hour post sunrise and 1 hour pre-sunset defined by within-subject meaningful change of 66 minutes increase from baseline to Week 26, will be analyzed using logistic regression analysis. The model will include the treatment group and the randomization stratification factors as fixed effect and the baseline average daily sunlight exposure time to first prodromal symptom as covariate. The treatment odds ratio at Week 26 will be estimated using a contrast. The missing data at Week 26 due to no available average daily sunlight exposure time to first prodromal symptom will be addressed as non-responder.

For each secondary efficacy endpoint, a subgroup analysis by region (North America, Europe, Japan, Australia) will be done.

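### Allocation ratio appears to depend on weight group, yet weight group does not appear among the factors in the readable secondary models

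*Protocol*

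**What the plan says.** **Allocation.** Protocol 7.1 limits the main scheme to subjects of at least 45 kg, who "will be randomized in a 1:1:1 ratio to receive MT-7117" at one of two doses or placebo. Protocol 8.3 sets the lower weight limit for entry at 30 kg. Protocol 11.5 adds a second scheme for a group whose label is redacted: "subjects will be randomized to placebo or [REDACTED] in a 1:2 ratio".

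**Stratification.** The baseline table in SAP 8.1.5 tags two rows as stratification factors: "Region (Randomization stratification factor") and baseline average daily time to first prodromal symptom. The weight row of that table is readable and is cut at <45 and ≥45 kg. It carries no such tag.

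**Models.** For the count of pain events (H5/H6), SAP 8.2.2 states: "The model will include treatment and the randomization stratification factors as fixed effect". The logistic model for responders (H9/H10) uses the same terms plus baseline time to symptom. The categorical terms of the primary MMRM in Protocol 14.3.2.1 and SAP 8.2.1 are partly redacted. SAP 8.2.2 reuses that model for PGIC and the PROMIS-57 domains.

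**Analysis set.** SAP 5.3 analyses all ITT subjects by randomised arm. No readable text limits the placebo comparator for either dose.

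**The concern.** If the 1:2 scheme applies to subjects of 30 to <45 kg, one dose can never be assigned to them. The three arms then differ systematically in their share of low-weight subjects. That share is highest in the dose offered to them, intermediate in placebo and zero in the other dose. A model without weight group carries any prognostic difference between the weight groups into both dose comparisons. In addition, the dose not offered is compared partly with placebo subjects who could not have been assigned to it. H5/H6 and H9/H10 are in the confirmatory fixed sequence, and the negative binomial model in the SAP has no baseline covariate that might absorb part of such a difference.

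**Working it through.** **The plan's own figures.** Protocol 14.2 states: "The sample size of 42 completers per treatment group will provide 91% and 79% power to detect an effect size of 0.72 and 0.66". Its inputs are a difference of 57 min for one dose and 52 min for the other, "and a standard deviation [SD] of 79.3 mins", two-sided alpha 0.05 and 20% dropout.
- Effect sizes: 57/79.3 = 0.72 and 52/79.3 = 0.66.
- Standard error with 42 completers per arm: 79.3 × √(2/42) = 17.3 min.
- Power for 57 min: Φ(57/17.3 − 1.96) = 90.9% by normal approximation, 90.2% by t test.
- Simulated fixed sequence (200,000 runs): 90.5% for the first test and 79.4% for both.
- Total: 42/0.8 = 52.5, rounded up to 53; 53 × 3 = 159.

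These reproduce. They assume three equal arms and do not mention the 1:2 group.

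**Arms under two schemes.** Let N = 184 (Protocol 8.1) and let k be the total number in the 1:2 group. The documents do not give k. Expected arm sizes are:
- placebo: (N − k)/3 + k/3 = N/3 = 61.3, unchanged because the placebo probability is one third under both schemes;
- dose offered: (N − k)/3 + 2k/3;
- other dose: (N − k)/3.

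**Shift if weight group is not in the model.** Let D be the difference in mean change between low-weight and other subjects on the same treatment. D is assumed to be 30 or 60 min.
- Dose offered: D × (share in that dose − share in placebo).
- Other dose: D × (0 − share in placebo).

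| k | Low-weight share: placebo / offered / other | Shift, D = 30 min | Shift, D = 60 min |
|---|---|---|---|
| 6 | 2/61.3 = 3.3% / 4/63.3 = 6.3% / 0 | +0.9 and −1.0 | +1.8 and −2.0 |
| 9 | 3/61.3 = 4.9% / 6/64.3 = 9.3% / 0 | +1.3 and −1.5 | +2.7 and −2.9 |
| 15 | 5/61.3 = 8.2% / 10/66.3 = 15.1% / 0 | +2.1 and −2.4 | +4.2 and −4.9 |

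In each cell the first figure is for the dose offered and the second for the other dose. If D is negative, the signs reverse.

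**Effect on type I error.** Take k = 15, D = 60 and 20% dropout, so 49.1 placebo and 45.1 other-dose completers. The standard error is 79.3 × √(1/49.1 + 1/45.1) = 16.4 min, and the shift is 4.9/16.4 = 0.30 standard errors. Two-sided error is Φ(−1.96 + 0.30) + Φ(−1.96 − 0.30) = 0.048 + 0.012 = 0.060. With up to 18 subjects and D up to half an SD (about 40 min) it stays at or below about 0.057. A deliberately extreme case (30 subjects, D of one SD, N = 184) gives shifts of +9.3 and −12.9 min and errors of 0.093 and 0.120.

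**Limits of this arithmetic.** The minutes refer to the primary endpoint, whose model may already contain weight group. They do not convert to the rate ratio (H5/H6) or the odds ratio (H9/H10). For those, only the unequal shares and the opposite directions carry over. No baseline adjustment is allowed for.

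**The case against.** The strongest reply is redaction. The label of the 1:2 group, the text introducing the stratum in Protocol 11.5, the randomisation text in SAP 3.1 and the MMRM terms are all blacked out. SAP 6.3 also points to a randomisation list specification that is not available here. SAP 8.1.5 describes summaries and does not specify the randomisation. A group with its own allocation list could be coded as a stratum without being tagged there, and the readable models would then already contain it.

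This stands for the primary MMRM and the models that reuse it. A reader might infer that the primary analysis omits weight group, but the documents do not show that. It is weaker for H5/H6 and H9/H10. Those models name only the stratification factors, the SAP's own tags identify two, and the weight row is readable and untagged.

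A reader might also infer that the other dose is compared with non-concurrent controls. Nothing says the 1:2 group enrolled at a different time. Its placebo subjects are concurrent; they simply could not have been assigned that dose.

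Two further replies have some force. The likely shift is small, and the readable baseline and baseline-by-visit terms of the MMRM may absorb part of it. The plan also makes the imbalance visible: weight category is summarised by arm, and SAP 8.2.1 analyses adolescents and adults separately. Neither replaces adjustment for a variable that sets the allocation probability.

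**Conclusion.** The point holds in a conditional form. Two allocation ratios exist, and weight group very probably decides which applies. On the SAP's own labelling, the H5/H6 and H9/H10 models do not appear to adjust for it. No readable text restricts the placebo comparator of the dose not offered to low-weight subjects.

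It would go too far to say that the comparisons are biased. That needs a prognostic difference, and the documents give neither its size nor the number of subjects. Under the assumptions above (6 to 15 subjects in total, 30 to 60 min), the shift on the primary scale is about 1 to 5 min. Compare assumed effects of 52 and 57 min and a standard error of about 17 min. This is probably small. The case for acting is that the analysis should follow the groups in which subjects were randomised, and that doing so costs very little.

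**What to change.** 1. State in the SAP whether the 1:2 group is a randomisation stratum and a model term.
2. If it is not, add weight group at randomisation (<45 versus ≥45 kg) as a fixed factor in the negative binomial and logistic models. Do the same in the MMRM-based models if it is not already there. Use the group that determined allocation; the SAP 8.1.5 row is weight at screening and could differ.
3. Add a sensitivity analysis comparing the dose not offered to low-weight subjects only with placebo subjects of at least 45 kg.

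**Cost.** The data are already collected, and the factor takes one degree of freedom. In the logistic model the stratum may be sparse: with 6 to 15 subjects, about 2 to 5 would be on placebo and 4 to 10 on the dose offered. A fallback such as penalised likelihood should therefore be named in advance. The restricted comparison loses little power. At the planned N of 159, for 52 min tested alone, it has 83.3% against 84.0% pooled with 6 low-weight subjects, and 80.1% against 82.4% with 18.
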